- **(ROC) curve analysis for discrimination between patients with TTP/HUS or SPE/HELLP using the IPF-%:** The optimal cutoff values for IPF-% for discrimination between patients with TTP/HUS or SPE/HELLP was >15.9 %. The sensitivity and specificity were 76.92% and 66.7%, respectively. The positive predictive value (PPV) and negative predictive value (NPV) were 55.6 % and 84.2%, respectively (AUC=0.692) (**Table 18**) (**Figure 23**).

Assessment of Immature Platelet Fraction in Pregnancy-Associated Thrombotic Microangiopathy: (Results)

[figure not shown]

Figure (23): Receiver-operating characteristic (ROC) curve analysis for discrimination between patients with TTP/HUS or SPE/HELLP using the IPF.

Assessment of Immature Platelet Fraction in Pregnancy-Associated Thrombotic Microangiopathy: (Results)

- **(ROC) curve analysis for discrimination between patients with TTP/HUS or SPE/HELLP using the schistocyte count:** The optimal cutoff values for schistocyte count for discrimination between patients with TTP/HUS or SPE/HELLP was $>4.6\%$. The sensitivity and specificity were 61.54% and 91.67% , respectively. The positive predictive value (PPV) and negative predictive value (NPV) were 80% and 81.5% , respectively (AUC=0.771) (Table 19), (Figure 24).

[figure not shown]

Figure (24): Receiver-operating characteristic (ROC) curve analysis for discrimination between patients with TTP/HUS or SPE/HELLP using the schistocyte count.

Comparison of the receiver-operating characteristic (ROC) curves:

Comparison of the receiver-operating characteristic (ROC) curves between IPF-% or schistocyte count revealed no significant difference between IPF-% and schistocyte count regarding discrimination between patients with TTP/HUS or SPE/HELLP (P-value >0.05) (Table 19), (Figure 25).

Assessment of Immature Platelet Fraction in Pregnancy-Associated Thrombotic Microangiopathy: (Results)

Table (19): Comparison of ROC curves for discrimination between patients with TTP/HUS or SPE/HELLP using the IPF or schistocyte count

Index	IPF	Schistocyte count	Difference	z	P-value¶
Area under ROC (AUC)	0.692 (0.519 to 0.833)	0.771 (0.603 to 0.893)	0.079 (-0.171 to 0.328)	0.617	0.537

Diagnostic indices are presented as value (95% CI).

¶DeLong method.

Assessment of Immature Platelet Fraction in Pregnancy-Associated Thrombotic Microangiopathy: (Results)

[figure not shown]

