Comparison of the receiver-operating characteristic (ROC) curves between IPF-% or schistocyte count for discrimination between patients with TMA and normal controls revealed no significant difference between IPF and schistocyte count regarding discrimination between patients with TMA and controls ($P > 0.05$) (Table 21), (Figure 28).

Table (21): ROC curves for discrimination between patients with TMA and normal controls using the IPF or schistocyte count

Index	IPF-%	Schistocyte count	Difference	z	P-value¶
Area under ROC (AUC)	0.820 (0.695 to 0.909)	0.838 (0.716 to 0.922)	0.018 (-0.105 to 0.142)	0.290	0.7722

Diagnostic indices are presented as value (95% CI).

¶DeLong method

Assessment of Immature Platelet Fraction in Pregnancy-Associated Thrombotic Microangiopathy: (Results)

[figure not shown]

Figure (28): ROC curves for discrimination between patients with TMA and normal controls using the IPF or schistocyte count.

✚ Correlation between IPF and schistocytes count with different parameters

no significant correlation was found between the IPF-% and schistocytes count in patients with SPE/HELLP, or TTP/HUS, as well as the whole TMA study group (**Figure 29**), (**Table 22**).

Table (22): Correlation between the IPF-% and schistocytes count in whole study population, patients with TMA, SPE/HELLP, or TTP/HUS, and normal controls

	Correlation between IPF % and schistocyte count		
Group	Number	Spearman rho (ρ)	P-value
TMA	37	0.231	0.169

Assessment of Immature Platelet Fraction in Pregnancy-Associated Thrombotic Microangiopathy: (Results)

SPE/HELLP	24	0.190	0.375
TTP/HUS	13	-0.058	0.851

[figure not shown]

Figure (29): Scatter plot showing the correlation between the IPF and schistocyte count in patients with SPE/HELLP or TTP/HUS.

IPF-% and schistocytes counts in TTP/HUS and SPE/HELLP using multivariate analysis

Assessment of Immature Platelet Fraction in Pregnancy-Associated Thrombotic Microangiopathy: (Results)

Multivariable binary logistic regression analysis was used for discrimination between patients with TTP/HUS or SPE/HELLP using the IPF-% and schistocyte count combined. Both IPF-% (odds ratio, 1.11; 95% CI, 1.010 to 1.220; $p=0.031$) and schistocyte count (odds ratio, 1.113; 95% CI, 1.016 to 1.219; $p=0.022$) were independent predictors for TTP/HUS.

Table (23): Multivariable binary logistic regression analysis for discrimination between patients with TTP/HUS or SPE/HELLP using the IPF and schistocyte count combined

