Variable	Regression coefficient (B)	SE for B	Wald	P-value	Odds ratio (OR)	95% CI for OR
IPF (%)	0.104	0.048	4.666	0.031	1.110	1.010 to 1.220
Schistocyte count (%)	0.107	0.046	5.283	0.022	1.113	1.016 to 1.219
Constant	-3.251					

Assessment of Immature Platelet Fraction in Pregnancy-Associated Thrombotic Microangiopathy: (Results)

Table (24): Receiver-operating characteristic (ROC) curve derived from the multivariable binary logistic regression model for discrimination between patients with TTP/HUS or SPE/HELLP using the IPF-% and schistocyte count combined

Sample size	37
Positive group (TTP/HUS)	13 (35.1%)
Negative group (SPE/HELLP)	24 (64.9%)
Disease prevalence (%)	35.1
<hr/>	
Index	Value
Area under the ROC curve (AUC)	0.827 (0.667 to 0.931)
z statistic	4.385
P-value	<0.0001
Sensitivity (%)	92.3 (64.0 - 99.8)
Specificity (%)	62.5 (40.6 - 81.2)
Positive likelihood ratio (+LR)	2.46 (1.4 - 4.2)
Positive likelihood ratio (-LR)	0.12 (0.02 - 0.8)
PPV, %	57.1 (34.0 - 78.2)
NPV, %	93.7 (69.8 - 99.8)

Diagnostic indices are presented as value (95% CI).

¶DeLong method.

Assessment of Immature Platelet Fraction in Pregnancy-Associated Thrombotic Microangiopathy: (Results)

[figure not shown]

Figure (30): Discrimination between patients with TTP/HUS or SPE/HELLP using IPF-% and schistocyte count combined.

Table 24 and Figure 30 shows the results of ROC curve analysis derived from the predicted probabilities as estimated from the multivariable binary logistic regression model for discrimination between patients with TTP/HUS or SPE/HELLP using the IPF and schistocyte count combined.

Table (25): Comparison of the receiver-operating characteristic (ROC) curves for discrimination between patients with TTP/HUS or SPE/HELLP using the IPF, schistocyte count, or IPF and schistocyte count combined

Marker	AUC	95% CI
IPF-%	0.692	0.519 to 0.833
Schistocyte count	0.771	0.603 to 0.893

Assessment of Immature Platelet Fraction in Pregnancy-Associated Thrombotic Microangiopathy: (Results)

IPF-% and schistocyte count combined 0.827 0.667 to 0.931

Marker	Difference between AUCs	95% CI	Z statistic	p-value
IPF-% vs. Schistocyte count	0.079	-0.171 to 0.328	0.617	0.537
IPF-% vs. IPF and Schistocyte count combined	0.135	-0.034 to 0.303	1.569	0.117
Schistocyte count vs. IPF-% and schistocyte count combined	0.056	-0.085 to 0.197	0.780	0.435

[figure not shown]

Figure (31): Discrimination between patients with TTP/HUS or SPE/HELLP.

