The model had good predictive value as evidenced by increased AUC of 0.827 (95% CI, 0.667 to 0.931). The estimated sensitivity was 92.3% (64.0% - 99.8%), specificity of 62.5% (40.6% - 81.2%), PPV of 57.1%

Assessment of Immature Platelet Fraction in Pregnancy-Associated Thrombotic Microangiopathy: (Results)

(34.0% - 78.2%), and NPV of 93.7% (69.8% - 99.8%). However, no statistically significant difference ($P > 0.05$) was revealed on comparing the AUC value of ROC curve of the combined use of IPF-% and schistocyte counts to AUC values of ROC curves of either marker alone for discrimination between patients with TTP/HUS or SPE/HELLP (Table 25, Figure 31).

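### Table 25 tests a fitted score against its own input markers in the same 37 women: the two P-values are unreliable, and the AUC gains are not corrected for optimism

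*SAP*

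**What the plan says.** The SAP is a results chapter. Its multivariate section fits a logistic model for TTP/HUS against SPE/HELLP on IPF-% and schistocyte count (Table 23) and states that both "were independent predictors for TTP/HUS", with Wald P=0.031 for IPF-% and 0.022 for schistocytes. The text on Table 24 presents the "results of ROC curve analysis derived from the predicted probabilities as estimated from the multivariable binary logistic regression model". The AUC is 0.827 (0.667 to 0.931), in the same 13 and 24 women.

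Table 25 compares that AUC with each input:

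- "IPF-% vs. IPF and Schistocyte count combined": gain 0.135 (-0.034 to 0.303), z=1.569, P=0.117.
- "Schistocyte count vs. IPF-% and schistocyte count combined": gain 0.056 (-0.085 to 0.197), z=0.780, P=0.435.

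Table 25 names no test. Its first row (IPF-% against schistocytes, z=0.617, P=0.537) repeats the result of "Table (19): Comparison of ROC curves for discrimination between patients with TTP/HUS or SPE/HELLP using the IPF or schistocyte count", which carries a DeLong footnote. I therefore take all three rows to be DeLong.

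The closing paragraph opens with "The model had good predictive value as evidenced by increased AUC of 0.827". It ends by stating, with P > 0.05, that nothing significant "was revealed on comparing the AUC value of ROC curve of the combined use of IPF-% and schistocyte counts to AUC values" for the single markers. Neither document describes validation, resampling or optimism correction. The protocol's Statistical methods section lists neither ROC nor logistic analysis.

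**The concern.** DeLong's test is built for two scores fixed before the data are seen. Here one score was estimated from the 37 outcomes it is then judged on, and it contains the marker it is compared with. Two separate problems follow.

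1. **Reference distribution.** If the added marker is useless, its coefficient is noise around zero and the combined score is almost a relabelling of the base marker. The AUC difference is then nearly degenerate, and z is not standard normal. A nominal 5% test can reject far less than 5% of the time.
2. **Optimism.** A score evaluated in its own fitting sample has an AUC that is too high on average, and so are its gains over the single markers.

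The protocol's aim is to show the utility of IPF-% and the absolute immature platelet count in differential diagnosis. Whether IPF-% adds to the blood smear bears directly on that. The closing paragraph speaks to it with an uncorrected AUC and with two tests that have little ability to reject.

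**Working it through.** **Step 1. Reproduce Table 25.** SE = (upper - lower)/3.92; z = difference/SE; P = 2(1 - Φ(z)).

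| Row | SE | z (printed) | P (printed) |
|---|---|---|---|
| IPF-% vs schistocytes | (0.328+0.171)/3.92 = 0.1273 | 0.079/0.1273 = 0.621 (0.617) | 0.535 (0.537) |
| IPF-% vs combined | (0.303+0.034)/3.92 = 0.0860 | 0.135/0.0860 = 1.570 (1.569) | 0.116 (0.117) |
| Schistocytes vs combined | (0.197+0.085)/3.92 = 0.0719 | 0.056/0.0719 = 0.778 (0.780) | 0.436 (0.435) |

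The arithmetic is sound, and each interval and P share one variance. What needs checking is the reference distribution.

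**Step 2. Behaviour under the null.** Simulation of 13 against 24 women, 8,000 datasets per scenario, with the logistic model refitted each time and DeLong applied to the fitted score against one input. Inputs from the SAP: AUCs 0.692 and 0.771, and weak within-group correlation ("no significant correlation was found between the IPF-% and schistocytes count in patients with SPE/HELLP, or TTP/HUS"; rho 0.190 and -0.058). Assumptions: normal markers with within-group correlation -0.2, 0 or 0.2; and three skewed sets matched to the SAP quartiles, schistocyte zeros (10/24 and 2/13) and cut-off counts, with the tails assumed.

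| Row and markers | Rejection at 1.96 | 5% critical value of absolute z | P for the printed z |
|---|---|---|---|
| IPF-% vs combined, normal | 0.20-0.44% | 1.31-1.33 | 0.015-0.021 |
| IPF-% vs combined, skewed | 0.22-0.42% | 1.29-1.31 | 0.016-0.019 |
| Schistocytes vs combined, normal | 0.10-0.22% | 1.28-1.31 | 0.265-0.280 |
| Schistocytes vs combined, skewed | 0.48-1.30% | 1.48-1.62 | 0.389-0.459 |

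Separate runs gave 0.016-0.027 and 0.020-0.036 for the IPF-% row, hence about 0.015 to 0.04 overall. For the schistocyte row another zero-inflated setting gave 0.31. Four more, with a schistocyte AUC of 0.81-0.85 (above the SAP's 0.771), gave 0.40-0.51.

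The mechanism shows in the normal-marker null. The root-mean-square DeLong SE was 0.039 against a true SD of 0.028 for the gain over schistocytes, and 0.058 against 0.040 for the gain over IPF-%. It is thus about 1.4 times too wide.

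**Step 3. Dependence on the base marker.** P for z=1.569 by true IPF-% AUC, normal markers:

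| True AUC | 0.52 | 0.55 | 0.60 | 0.65 | 0.692 | 0.75 |
|---|---|---|---|---|---|---|
| P | 0.103 | 0.068 | 0.039 | 0.024 | 0.021 | 0.016 |

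A skewed setting at 0.55 gave 0.080. At 0.52 the test is almost correctly sized (4.8% rejection, critical value 1.94). The printed interval for the IPF-% AUC is 0.519 to 0.833, so the weak end is not excluded.

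**Step 4. Optimism.** Both markers informative, 2,500 datasets, with 1,200 fitted scores re-evaluated in 25,000 new cases and 25,000 new non-cases. The independent normal scenario reproduces the SAP closely:

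| Quantity | SAP | Simulated in-sample mean | Simulated, new women | Optimism |
|---|---|---|---|---|
| Combined AUC | 0.827 | 0.828 | 0.804 | 0.024 |
| Gain over IPF-% | 0.135 | 0.135 | 0.111 | 0.024 |
| Gain over schistocytes | 0.056 | 0.057 | 0.029 | 0.028 |

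Over all scenarios the optimism was 0.016-0.032, 0.012-0.034 and 0.019-0.031 respectively. The DeLong 95% intervals covered the new-data gain 90-95% of the time over IPF-% and 87-93% over schistocytes.

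**Step 5. Power.** With both markers truly informative (4,000 datasets per scenario), DeLong rejected in about 19-27% of datasets against IPF-% and 2-4% against schistocytes. A non-significant result is what one expects even when IPF-% contributes.

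**The case against.** The strongest reply is that the SAP does not claim what a critic would want to refute. It reports no significant AUC difference; it never says that IPF-% adds nothing. It calls both markers independent predictors, and its intervals, reaching +0.303 and +0.197, already leave room for a gain. That stands. A coefficient test and an AUC comparison also use different measures, so the two statements are not a contradiction. What remains is that the AUC statement rests on a test that does not have its nominal size.

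A reader might infer that both printed P-values are too large. The documents do not support that for P=0.435. It looks too large only if the markers are roughly normal, and the SAP's schistocyte medians and quartiles, 0.5 (0.0 to 1.2) and 6.5 (0.8 to 17.6), are plainly skewed. In the skewed sets matched to the SAP the recalibrated value lies on either side of 0.435.

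The correction to P=0.117 is conditional too, as Step 3 shows. The optimism is small beside standard errors of 0.086 and 0.072, which is fair, though it is about half of the 0.056 gain over schistocytes. Finally, the Table 23 Wald tests are unplanned, come from the same women and are somewhat conservative themselves (null rejection 1.4-4.0%). That also stands, and it limits them to exploratory use.

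**Conclusion.** The defect holds. Two rows of Table 25 apply what appears to be a DeLong test to a nested, in-sample comparison for which its z is not standard normal, and the combined AUC and both gains are uncorrected.

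- **IPF-% against combined:** P=0.117 is probably too large. Whether P > 0.05 survives depends on how informative IPF-% is alone.
- **Schistocytes against combined:** P=0.435 may be too large (about 0.27 with normal markers) or about right (about 0.39 to 0.46 with skewed ones). It is non-significant either way.
- **Optimism:** about 0.01 to 0.03 on each quantity; the gain over schistocytes may fall from 0.056 to about 0.03.

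A reader might infer that recalibration shows IPF-% to add to the smear. It does not: the row that may become significant concerns schistocytes added to IPF-%. The data neither establish nor exclude an AUC gain from IPF-%.

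Confidence is high on the defect and medium on the numbers, which rest on assumed marker distributions and on DeLong being the test used. Exact values need the patient data. The IPF-% against schistocyte row compares two unfitted markers and is unaffected.

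**What to change.** 1. In Table 25 remove z, P and interval from the two rows that involve the combined score. Keep the IPF-% against schistocyte row (P=0.537) and add a footnote naming its method.
2. Report the combined AUC and both gains as bootstrap optimism-corrected estimates with intervals, refitting the logistic model in each resample.
3. Use the Table 23 coefficient tests (Wald, or likelihood ratio) as the test of added value, labelled unplanned and exploratory with 13 TTP/HUS cases. Say which test is used: in the null simulations Wald rejected about 1-4% and likelihood ratio 6-8%.
4. Reword the closing paragraph to give the corrected AUC and gains in place of the in-sample increase, and to say that whether IPF-% adds to the schistocyte count is unsettled.

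The cost is a little reanalysis of existing data and no new patients. The combined AUC will probably come out below 0.827, and the intervals will be wide.
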